5.3.2. Other Secondary Efficacy Endpoints

- Time to all-cause mortality through Week 16
- Incidence of and time to all-cause mortality through Week 36
- Incidence of and time to non-relapse mortality through Weeks 16 and 36
- Incidence of and time to AdV-associated mortality through Weeks 16 and 36, where mortality is assessed by a blinded EAC
- Proportion of subjects with undetectable AdV viremia at Weeks 2, 4, 6, 12, and 16
- Proportion of subjects with $\geq 2\text{-log}_{10}$ decline from baseline or undetectable AdV viremia at Weeks 2, 4, 6, 12, and 16
- Proportion of subjects with $\geq 1\text{-log}_{10}$ decline from baseline or undetectable AdV viremia at Weeks 2, 4, 6, 12, and 16
- AAUC at Weeks 2, 4, 6, and 12
- Incidence of and time to first confirmed undetectable AdV viremia
- Incidence of and time to virologic relapse (subsequent confirmed AdV viremia ≥ 1000 copies/mL) among subjects with confirmed clearance of AdV from plasma (overall; by AdV in urine, stool, and respiratory secretions at the time of first undetectable AdV viremia; and by T cell-mediated immune function [e.g., CD4+ cells $>$ or ≤ 50 cells/ μL] at the time of first undetectable AdV viremia)
- Maximum PELOD score through Week 16
- Number of days spent in the hospital through Week 16
- Number of days spent in the ICU through Week 16
- Emergence of AdV mutations associated with genotypic resistance and phenotypic resistance (the latter when possible) to BCV or CDV
- Incidence of and time to progression to probable or definitive AdV disease (among asymptomatic subjects at baseline)
- Incidence of and time to resolution of AdV clinical disease (among subjects with probable or definitive AdV disease at baseline)

- Primary model-based PK parameters, such as apparent clearance (CL/F), intercompartmental clearance (Q/F), volume of central compartment (V_c/F), volume of peripheral compartment (V_p/F), absorption rate constant (K_a), and lag time (T_{lag}), secondary PK parameters, such as C_{max} and area under the plasma concentration time curve at steady state (AUC_{ss}), and identification of covariates that influence these PK parameters
- Relationship between plasma BCV exposure, other covariates of interest, and
 - safety endpoints, including GI AEs, diarrhea, ALT, total bilirubin, and other safety events of interest
 - virologic endpoints including AAUC, AAUCMB, viral load change from baseline, and other virologic endpoints of interest,

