12.4. Efficacy Analyses

12.4.1. Primary Efficacy Endpoint

The primary AAUC analysis will utilize all randomized subjects (ITT) in an analysis of covariance (ANCOVA) with all stratification factors included in the model: T cell-depletion method (alemtuzumab or ex vivo cell selection vs. ATG), time from HCT to randomization (< 28 days vs. \geq 28 days), and baseline AdV viremia (continuous \log_{10} copies/mL). These stratification factors have been selected as those that are clearly related to time to immune reconstitution (time from HCT to confirmed AdV viremia > 1000 copies/mL and thus randomization, procedural differences in depth and duration of immune suppression by T cell-depletion method) with resulting expected differences in clearance of viremia, and/or association with mortality (peak viral load). Regarding baseline AdV viremia, subjects will be stratified at the time of randomization according to \geq 10,000 vs. < 10,000 copies/mL; however, this factor will be included in the analysis as a continuous covariate in order to improve power in determining a treatment effect. In the ANCOVA, AdV viremia values that are undetectable will be imputed at 99 copies/mL (i.e., one less than the lower limit of detection of 100 copies/mL) and values that are detected, but not quantifiable (BLQ) will be imputed at 189 copies/mL (i.e., one less than the lower limit of quantification of 190 copies/mL).

Subjects who die or are lost to follow-up (i.e., drop-outs) prior to Week 16 are accounted for inherently in the AAUC approach by truncating their follow-up period, thereby normalizing AUC over time of follow-up (Li 2012). It should be noted that subjects lost to follow-up are anticipated to be zero or negligible, and approximately 16% to 24% of subjects are expected to die by Week 16. Regardless, the primary analysis will be supplemented by a number of planned sensitivity analyses to assess the impact of subjects who die prior to Week 16 and other potential influential elements on the primary inference and to allow for a more comprehensive assessment of efficacy.

The first three approaches are proposed to account for these subjects in a typical missing data framework:

- Jump to reference imputation, where the missing part of the trajectory is imputed from the control group average ([Kenward 2015](#)).

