12.4.2. Secondary Efficacy Endpoints

Continuous secondary efficacy analyses will use the same method used for the primary analysis.

Dichotomous secondary efficacy analyses will be analyzed using a Cochran-Mantel-Haenszel test stratified by each of the stratification factors. Number of failures and failure rates will be presented for each treatment arm. Cochran-Mantel-Haenszel p-values, estimated common odds ratios, and corresponding approximate 95% CIs will be presented for each comparison. The Breslow-Day test will be used to test the homogeneity of the odds ratios. Missing data will be imputed as failure.

Most time-to-event analyses will be performed using Kaplan-Meier methods/plots and Cox models. P-values and hazard ratios along with their 95% CIs will be presented for each treatment comparison. Missing data will be censored, generally at the earlier of the end of study for each subject or the time point for the specific analysis.

Non-relapse mortality will be analyzed with relapse as a competing risk adjusted for baseline strata, with corresponding cumulative incidence plots, Fine-Gray models, and cause-specific and sub-distribution hazard ratios with corresponding 95% CIs.

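### The missing = failure rule in 12.4.2, applied to progression and relapse with no stated rule for death, would make the incidence odds ratio partly a mortality comparison

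*Combined protocol and SAP*

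**What the plan says.** Section 5.3.2 lists progression as one endpoint with two readouts: "Incidence of and time to progression to probable or definitive AdV disease (among asymptomatic subjects at baseline"). Virologic relapse after confirmed clearance has the same two-part form. Neither carries a time point.

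Section 12.4.2 then gives one general rule per readout. Dichotomous endpoints go to a Cochran-Mantel-Haenszel analysis, reported as failures and failure rates: "estimated common odds ratios, and corresponding approximate 95% CIs will be presented for each comparison". The rule for gaps is "Missing data will be imputed as failure". For the other readout, "Most time-to-event analyses will be performed using Kaplan-Meier methods/plots and Cox models", and "Missing data will be censored, generally at the earlier of the end of study for each subject", or at the analysis time point if that comes sooner. The only competing-risk provision is for another endpoint: "Non-relapse mortality will be analyzed with relapse as a competing risk adjusted for baseline strata".

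Section 12.4.2 does not mention death before progression or relapse. The nearest guidance is in 12.4.1, for the primary endpoint AAUC. It takes deaths and drop-outs together and says: "The first three approaches are proposed to account for these subjects in a typical missing data framework". It expects next to no loss to follow-up, but "approximately 16% to 24% of subjects are expected to die by Week 16".

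**The concern.** Missing = failure suits a response endpoint: a child with no result has not been shown to clear the virus. Progression and relapse run the other way, because the failure is the event. Imputing failure there creates events that nobody observed.

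With loss to follow-up near zero, the rule has little to act on except deaths. If deaths fall under it, the incidence table reports progression-or-death under the name of progression, and any mortality difference between arms feeds into its odds ratio. The hazard ratio for the same named endpoint treats those children differently. A reader comparing the two would be looking at different quantities without being told. An effect on AdV disease could appear, or be diluted, because of deaths unrelated to AdV.

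**Working it through.** **The plan's own figure.** Sections 12.1 and 12.4.1 assume SoC mortality of 20% to 30% and an advantage of 6 to 9 points, so BCV mortality is 14% to 21%. With 94 and 47 subjects:

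- (94 × 0.14 + 47 × 0.20)/141 = 22.56/141 = 16.0%
- (94 × 0.21 + 47 × 0.30)/141 = 33.84/141 = 24.0%

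This reproduces the stated 16% to 24%.

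**Assumptions not in the documents.** Net progression q is 15% in both arms (no treatment effect). Progression and death have independent constant hazards. Whole-trial mortality m applies to children asymptomatic at baseline. For precision, those children number 47/24 to 70/35 (BCV/SoC), about half to three quarters of each arm.

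**Formulas.** λp = −ln(1 − q) and λm = −ln(1 − m).

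- Progression only: λp/(λp + λm) × [1 − exp(−(λp + λm))]
- Deaths imputed as failure: 1 − exp(−(λp + λm)) = q + (1 − q)m

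Here λp = 0.1625, and λm = 0.1508, 0.2231, 0.2357 and 0.3567 for mortality of 14%, 20%, 21% and 30%. For example, BCV at 14% mortality gives 0.15 + 0.85 × 0.14 = 26.9%.

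| Mortality BCV/SoC | Progression only BCV/SoC | OR | Deaths as failure BCV/SoC | OR | Deaths as share of failures BCV/SoC |
|---|---|---|---|---|---|
| 14%/20% | 14.0%/13.5% | 1.04 | 26.9%/32.0% | 0.78 | 48%/58% |
| 21%/30% | 13.4%/12.7% | 1.07 | 32.85%/40.5% | 0.72 | 59%/69% |

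**Against sampling error.** The arm difference shifts by 5.6 and 8.4 points. The standard error of the imputed analysis is 9.5 to 12.1 points, so the shift is 0.48 to 0.84 standard errors.

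**Other progression rates.** For q from 5% to 40%, the imputed odds ratio is 0.71 to 0.87 at 14%/20% and 0.66 to 0.80 at 21%/30%.

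**Deaths that follow progression.** The model above puts about 92% of deaths before any progression (12.9 of 14 points in BCV at 14% mortality). Suppose instead that half the deaths at 14%/20% come after progression, with 13.5% progressing in each arm. Failures are then 13.5 + 7 = 20.5% and 13.5 + 10 = 23.5%, and the odds ratio is (0.205/0.795)/(0.235/0.765) = 0.84.

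**A true effect, assumed 10% vs 30% net progression.** Power is taken as Φ(difference/SE − 1.96) with 70/35 subjects and unpooled SE.

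- Mortality 14%/20%: incidence 9.3% vs 27.1%, OR 0.28. Imputed, 22.6% vs 44.0%, OR 0.37. Power goes from Φ(0.178/0.0827 − 1.96) = 58% to Φ(0.214/0.0977 − 1.96) = 59%.
- Mortality 20%/20%: incidence 9.0% vs 27.1%, OR 0.27. Imputed, 28.0% vs 44.0%, OR 0.49. Power goes from Φ(0.181/0.0825 − 1.96) = 59% to Φ(0.160/0.0996 − 1.96) = 36%. With a pooled null variance the fall is from 67% to 38%.

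No calculation was made for virologic relapse. The logic is the same, but its size is not estimated here.

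**The case against.** The strongest reply is that nothing in the document calls death missing data for these endpoints. The missing-data approaches in 12.4.1 concern AAUC trajectories, and the same section adds three analyses that account for deaths directly. The per-protocol set in 12.2 keeps children who die before Week 16, and the safety-review triggers in 12.3 list death separately from loss to follow-up. A child followed to death without AdV disease can be read as an observed non-progressor, who adds no event to either readout. Section 12.4.2 is also worded for most analyses and generally, and Section 12 leaves detail to the SAP.

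That much stands: the classification of deaths is an inference. A reader might conclude that the plan declares such a child a progression; it does not go that far. But the failure rule is written without exception, the AAUC precedent points towards deaths being missing, and the alternative reading is nowhere stated. In an open-label trial the choice should not be left open.

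A reader might also infer that the Cox analysis scores the child as a non-progression, so that the hazard ratio would contradict the odds ratio. Censoring only ends observation; the two results would answer different questions. Nor do the plan's own mortality assumptions support a general loss of power. In the example above the loss appears with equal mortality, not at 14%/20%.

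The independence model is near the unfavourable end. Section 4.1 ties high mortality to disseminated AdV disease, so more deaths may follow progression than it allows. Finally, these are two of many other secondary endpoints, the only sequential testing described is for mortality, and mortality is reported separately.

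**Conclusion.** The concern holds as a rule carried over to endpoints it does not fit, together with a missing definition of how death is handled. If deaths are treated as missing, as 12.4.1 does for AAUC, the incidence odds ratio for progression partly measures mortality. With no effect on progression it would be about 0.78 or 0.72 rather than 1.04 to 1.07, and roughly half to two thirds of the reported events would be deaths. These figures rest on an assumed 15% progression rate, independence of death and progression, and whole-trial mortality in the asymptomatic subset. The distortion shrinks as more deaths follow progression.

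The document does not support saying that the trial's main conclusions are at risk. It is a cheap improvement to secondary analyses.

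**What to change.** In Section 12.4.2:

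- Limit missing = failure to response endpoints: undetectable viremia, log10 decline, confirmed clearance and disease resolution.
- For progression and relapse, state the time point and treat death without the event as a competing event in both readouts. Report cumulative incidence by arm with cause-specific and Fine-Gray hazard ratios, as already planned for non-relapse mortality.
- Report progression-or-death and relapse-or-death as separately labelled composite sensitivity analyses.
- State a rule for the few true drop-outs.

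The cost is a few sentences and one extra table, with no new data. Counting only the event slightly favours an arm with more early deaths, as the 1.04 to 1.07 above shows; the composite makes that visible. The change should precede the primary database lock, since Section 12 treats later changes as post hoc.

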- Multiple imputation, where the missing part of the trajectory is imputed based on a model ([Rubin 1978](#)). This imputation is repeated to create multiple simulated data sets (e.g., 5-times the number of deaths plus drop-outs). Each of these simulated data sets is analyzed independently and the results from these analyses are pooled to yield a final inference.
- Undetectable imputation, where the missing part of the trajectory is imputed as undetectable.

In addition to the above, three other supportive analyses are proposed to directly account for subjects who die prior to Week 16:

- Baseline imputation, where the missing part of the trajectory for deaths only is imputed at the baseline value for the subject.
- Analysis of time below the detection limit, whereby subjects who die are considered to be above the detection limit after death. This approach will be repeated using time below 1000 copies/mL, which is a clinically-meaningful level of viremia often signaling viral control vs. need to address in clinical practice.
- Generalized pairwise comparisons of prioritized outcomes ([Buyse 2010](#)). In this approach, all BCV subjects are compared with all SoC subjects in the same stratum. Comparisons will be made based on the following hierarchy:
 - Alive or dead at Week 16
 - If both die before Week 16, compare time to death
 - If both are alive at Week 16, compare AAUC

Each comparison yields a favorable, unfavorable, or neutral result. The “proportion in favor of treatment” (Δ) is the net difference between the number of favorable pairs and the number of unfavorable pairs divided by the total number of pairs. The null hypothesis $H_0: \Delta=0$ is tested using a randomization test.

Another important factor that may influence the primary inference is the imputation of undetectable and BLQ AdV viremia values, with additional sensitivity analyses conducted in order to assess the potential impact of this imputation:

- Impute all undetectable/BLQ values at 1 copy/mL (i.e., 0 log₁₀ c/mL)
- Impute all undetectable/BLQ values at 189 copies/mL
- Impute all values < 1000 copies/mL at 1 copy/mL

In addition, a supportive analysis of overall mortality (adjusting for advanced baseline disease, [Matthes-Martin 2008](#)) will examine the non-inferiority of BCV treatment to SoC. No negative impact on mortality will be concluded if the upper bound of the one-sided 95% confidence

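### If deaths are censored, as Section 12.4.2 applied as written would most naturally do, the Kaplan-Meier curves for viral clearance and related endpoints overstate cumulative incidence

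*Combined protocol and SAP*

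**What the plan says.** Section 12.4.2 (repeated in the synopsis) sets one general rule: "Most time-to-event analyses will be performed using Kaplan-Meier methods/plots and Cox models". On incomplete follow-up it says "Missing data will be censored, generally at the earlier of the end of study for each subject", or at the analysis time point if that comes first. One exception is spelled out: "Non-relapse mortality will be analyzed with relapse as a competing risk adjusted for baseline strata", with cumulative incidence plots, Fine-Gray models, and cause-specific and sub-distribution hazard ratios.

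Section 5.3.2 lists five other time-to-event endpoints that a death can preclude: first confirmed undetectable viremia, virologic relapse, progression to AdV disease, resolution of AdV disease, and AdV-associated mortality (precluded by a death from another cause). Section 12.4.2 does not say how death enters any of them.

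Section 12.4.1 does deal with death, but for the primary AAUC endpoint. On follow-up to Week 16, its expectation reads: "subjects lost to follow-up are anticipated to be zero or negligible, and approximately 16% to 24% of subjects are expected to die". It states that "Subjects who die or are lost to follow-up (i.e., drop-outs) prior to Week 16 are accounted for inherently in the AAUC approach", because follow-up is truncated. It adds sensitivity analyses: "The first three approaches are proposed to account for these subjects in a typical missing data framework"; a baseline imputation "where the missing part of the trajectory for deaths only is imputed at the baseline value for the subject"; and, including that one, "three other supportive analyses are proposed to directly account for subjects who die prior to Week 16". One of those last three counts a child who has died as above the detection limit from then on.

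Section 12 leaves detailed methods to the SAP, which may be amended until the primary database lock.

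**The concern.** A child who dies before clearing the virus cannot clear it later. If that child is censored at death, the Kaplan-Meier method treats the child as still able to clear, at the same rate as the survivors. 1-KM then estimates clearance in a hypothetical setting without deaths, not the share of children who clear. The same applies to relapse, progression and resolution, and to AdV-associated death when the child dies of something else.

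The stake is limited to the absolute height of these curves and to figures read from them. A Week 16 clearance percentage read from the curve would exceed the true proportion. It would also disagree with the incidence reported for the same endpoint under the dichotomous rule, which imputes missing outcomes as failures. A reader of the report would see two clearance figures for one endpoint, with no stated reason for the gap.

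**Working it through.** **Would deaths be censored?** The rule takes the earlier of two dates. For a child who dies before Week 16, the end of study comes first. With loss to follow-up expected to be negligible, nearly every early end of follow-up would be a death. Section 12.4.1 also places deaths beside drop-outs and calls what follows a death missing. This makes censoring the natural reading; it is not a stated rule.

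**Direction.** Let Hc be the cumulative cause-specific hazard of clearance. 1-KM integrates exp(-Hc) dHc. The cumulative incidence integrates S dHc, where S is the probability of being alive and not yet cleared. S never exceeds exp(-Hc), so 1-KM is never below the cumulative incidence, and it is above it once deaths precede later clearances. This does not depend on independence or constant hazards.

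**Mortality inputs.** Section 12.4.1 assumes SoC mortality of 20% to 30% and a BCV advantage of 6 to 9 points, so BCV mortality is 14% to 21%. Pooling over 94 and 47 subjects reproduces the plan's own figure:

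- (94 x 0.14 + 47 x 0.20) / 141 = 16.0%, about 23 deaths
- (94 x 0.21 + 47 x 0.30) / 141 = 24.0%, about 34 deaths

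**Clearance inputs.** Section 4.4 reports median times to clearance of 4 weeks (BCV) and 9 weeks (IV CDV). I assume these are net medians, meaning medians in the absence of death, and that the IV CDV figure represents SoC. They may be medians among clearers only.

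**Formulas**, with constant independent weekly hazards:

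- hc = ln 2 / median; hd = -ln(1 - mortality) / 16
- 1-KM at Week 16 = 1 - exp(-16 hc)
- Cumulative incidence at Week 16 = hc / (hc + hd) x [1 - exp(-16 (hc + hd))]

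| Arm | Mortality | hc | hd | 1-KM | Cumulative incidence | Excess (points) | Children |
|---|---|---|---|---|---|---|---|
| BCV | 14% | 0.1733 | 0.0094 | 93.8% | 89.7% | 4.0 | 3.8 of 94 |
| BCV | 21% | 0.1733 | 0.0147 | 93.8% | 87.6% | 6.1 | 5.8 of 94 |
| SoC | 20% | 0.0770 | 0.0139 | 70.8% | 64.9% | 5.9 | 2.8 of 47 |
| SoC | 30% | 0.0770 | 0.0223 | 70.8% | 61.7% | 9.1 | 4.3 of 47 |

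A simulation of 4,000 trials per row gave the same mean excess to within 0.1 point. The median moves less: from 4.0 to 4.1 or 4.2 weeks for BCV, and from 9.0 to 9.8 or 10.4 weeks for SoC.

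**Other clearance assumptions, same mortality:**

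- BCV median of 12 to 22 days (Section 4.3.3.2): excess 2.3 to 5.5 points.
- Hazards solved so that 15 of 18 (BCV) and 8 of 23 (SoC) clear by Week 16, taking the Figure 8 counts as all clearers: BCV 4.3 to 6.5, SoC 3.7 to 5.9.
- Net medians of 3 to 6 weeks (BCV) and 7 to 16 weeks (SoC): 3.5 to 6.6 and 4.6 to 9.6.

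**AdV-associated death.** If a share s of deaths is AdV-related at a constant ratio, the excess is [1 - (1 - m)^s] - s m, where m is mortality. The plan does not assume a share.

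- s = 0.5: 0.3 points (m = 14%), 0.6 (20%), 0.6 (21%), 1.3 (30%).
- s = 0.15, the share of all mortality reported for one cohort in Section 4.3.7.2: 0.1 points (14%) to 0.7 (30%).

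Relapse, progression and resolution cannot be sized, because the documents give no usable event rates for them.

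**The case against.** The strongest reply is that no sentence says deaths are censored. Section 12.4.2 is hedged (most analyses, generally), speaks of missing data, and a known death need not be missing. Detail is left to a SAP that may already settle the point. Non-relapse mortality gets competing-risk methods, and one supportive analysis of the primary endpoint treats dead children as not cleared, so the sponsor plainly knows the problem. The AAUC truncation rule also belongs to the primary endpoint and cannot settle what happens to a secondary one. All of this stands, and it is why the point is conditional.

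It could also be argued that deaths are carried to Week 16 as non-events, which would make the Week 16 value correct. The rule's choice of the earlier date rules that out as written.

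A further reply is that the dichotomous analysis already gives the clearance proportion with missing outcomes as failures. That is true and limits the harm, but it leaves the curve, which would contradict it.

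A reader might infer more than the documents support:

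- **That the trial's main conclusions are at risk.** They do not use these curves.
- **That the bias favours one arm.** The SoC excess is larger in the base case and smaller when calibrated to the Figure 8 counts, so the direction is not determined.
- **That the excess could reach about 12 points.** The BCV figure reaches 11.7 only if two thirds of deaths precede clearance. The base case implies about 35%, and the documents do not say when deaths fall relative to clearance.

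**Conclusion.** The point holds as a gap in the stated method with a predictable consequence, not as a proven analysis error. Applied as written, Section 12.4.2 would most naturally censor deaths, and the 1-KM curves would then overstate cumulative incidence. The direction is certain once deaths are censored.

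The size is illustrative: about 4 to 6 points for BCV and 6 to 9 for SoC for Week 16 clearance. It rests on constant independent hazards, the Section 4.4 medians read as net medians, and the plan's own mortality assumptions. AdV-associated death is a minor case at about 1 point or less, and the remaining three endpoints are affected in principle only.

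Primary, key secondary and Cochran-Mantel-Haenszel results are untouched, and Cox hazard ratios with deaths censored remain valid if read as cause-specific. The change is worth making because it is cheap and the plan already uses the right tools for non-relapse mortality.

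**What to change.** Add to Section 12.4.2 and the SAP, before database lock:

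- For time to first confirmed undetectable viremia, virologic relapse, AdV disease progression and AdV disease resolution, death before the event is a competing event.
- For AdV-associated mortality, a death that the adjudication committee does not attribute to AdV is a competing event.
- For these endpoints, Aalen-Johansen cumulative incidence curves by arm replace 1-KM.
- Cox hazard ratios for these endpoints are labelled cause-specific.

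Kaplan-Meier stays for all-cause mortality. Fine-Gray ratios are optional; they are not needed to correct the curves.

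The cost is wording and slightly more programming, with no new data. The reported clearance curves will be lower than under 1-KM.
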